3.2 Safety Objective

The safety objective of this study is to capture existing Gentrax Surgical Matrix Complication data in the later post-operative period to date, not previously reported in the T-GENVIH-002 study.

Gentrax® Surgical Matrix Complications are defined but not limited to:

- Seroma
- Abscess
- Dehiscence
- Hematoma
- Wound necrosis
- Ileus
- Fistula
- Delayed wound healing

3.3 Primary Endpoint

The primary endpoint of this prospective study is to determine the incidence of clinically confirmed recurrence of the primary hernia to date, including not previously reported in T-GENVIH-002 study.

3.4 Secondary Endpoints

1. Incidence of self-reported recurrence (i.e., bulge) of the primary hernia to date, including not previously reported in T-GENVIH-003 study.
2. Incidence of Surgical Site Occurrences requiring procedural intervention (SSOPI) of the primary hernia repair to date, not previously reported in T-GENVIH-002.
3. Incidence of Surgical Site Occurrences (SSOs) of the primary hernia repair to date (seroma, abscess, dehiscence, hematoma, wound necrosis, ileus, fistula, delayed wound healing), including not previously reported in T-GENVIH-002 study.
4. Incidence of Surgical Site Infections (SSIs) post primary hernia repair to date, including not previously reported in GENVIH-002 study.
5. Incidence of reoperation requirement of the primary hernia repair to date, including not previously reported in GENVIH-002 study.

4 Study Design

4.1 Overall Design

The Gentrix Ventral Hernia Repair Long Term Follow Up study is a single-arm, prospective, single-center, post-market study which includes Long Term Follow Up (LTFU) safety and performance outcomes of a sub-population of subjects who underwent minimally invasive (e.g., laparoscopic or robotic) surgical repair using Gentrix® Surgical Matrix post index procedure to date, including not previously reported in T-GENVIH-002 study.

4.2 Scientific Rationale for Study Design

This study adds to the available data evaluating the safety and effectiveness of Gentrix Surgical Matrix in ventral hernia repair, particularly in a real-world population, and particularly in the MIS sub-population described.

4.3 End of Study Definition Overview

The end of the study is defined as completion of Case Report Forms (CRFs) for the last subject in this prospective study.

5 Study Population

5.1 Inclusion Criteria

1. Patient was a subject in the T-GENVIH-002 study and underwent minimally invasive (i.e., laparoscopic or robotic) surgical abdominal wall reconstruction for a primary hernia repair using Integra Gentrix® Surgical Matrix.
2. Subject has participated in the informed consent process and signed a study-specific informed consent document.
3. Subject is fluent in US English or US Spanish language.
4. Subject is willing to complete an e-consent and phone or in-office visit.

5.2 Exclusion Criteria

Not applicable.

5.3 Description of the site

One site in the US will be selected to participate in this study. The study site was selected based upon their prior participation in the T-GENVIH-002 study, experience with the subject device, their clinical expertise, expected commitment to have available data for eligible study patients, and their ability to fulfill general requirements in the Sponsor's SOPs and to comply with this protocol.

5.4 Point of Enrollment & Enrollment Period

The patients will provide informed consent to allow use of their data. There is no traditional enrollment period in this study. Data will begin to be collected from the first patient who meets all the eligibility criteria.

The total expected duration of the study is approximately 3 months.

5.5 Strategies for Recruitment

A one-off subject phone (call) visit will constitute the source of data and will be collected using a study-specific eCRF delivered via a phone script by the site responsible or their designee(s). Each patient should be included in the study only once. Patient screening will rely on site identification and contact of prior T-GENVIH-002 study subjects (Sponsor remains blinded) and e-consent process. In these cases, every effort should be made to identify every possible eligible patient. For those that are lost to follow up, site may work directly with a Sponsor approved people search service (Sponsor remains blinded). In order to be eligible for the study, patients should meet all of the eligibility criteria.

For subjects who decline an electronic consent collected remotely, an in-office interview and assistance with completing the electronic consent in person with the site study coordinator or their designee(s) will be offered for the convenience of the subjects and to maximize data collection efforts.

5.6 Risk/Benefit Assessment

5.6.1 Risks associated with Study device

Complications and reactions are possible with any soft tissue repair, including but not limited to infection, increased chronic inflammation, allergic reaction, unexplained fever or chills, excessive redness, acute and chronic pain, swelling, tender scars, adhesions, seroma formation, fistula formation, hematoma, recurrence of tissue defect, delayed or failed

incorporation of graft, urinary or fecal incontinence, delayed or failed incorporation of graft (mesh) or suture erosion or extrusion, and injury to the bladder, bowel, blood vessels.

5.6.2 Risks Associated with Participation in the study and mitigation

As this prospective study involves data collection, there are only minimal risks associated with participation. There are no additional device-related risks for this study. There are, however, privacy (loss of confidentiality) risks associated with participation in the study.

Participation in the study does not submit the patient to any additional procedures or exams outside the customary standard of care. Patient confidentiality and privacy is strictly held in trust by the participating investigator, their staff, and the Sponsor. The patient's data will be given a code to assure that the data can only be traced with the use of an identifier. The identifier will be stored securely in the local research institute. Data that is shared with the sponsor will only contain the code. The patient's name and any other identifiable information will be omitted. All national data protection laws will be respected including the US Health Insurance Portability and Accountability Act of 1996 (HIPAA). Data shared with the Sponsor will be encoded and maintained in a secure electronic database that is compliant with 21 CFR Part 11 requirements on electronic records and electronic signatures.

5.6.3 Anticipated Clinical and device Benefits

There is no direct benefit. Information learned from this study might help researchers to better understand medical treatments and disease processes or procedures in order to better help others in the future.

The data collected from the study will be used to inform the device manufacturer about the safety and performance of the device when used in accordance with the device labelling.

5.6.4 Rationale of Risks/Benefits Ratio

The participation in the study does not add risks to the patients, thus the benefit is judged to outweigh the overall residual risks.

6 Study Assessments and Procedures

6.1 Schedule of Data Collection

6.1.1 Eligibility/Consent

- The procedures to be completed are:

- ✓ Identification of the full consecutive series of patients who underwent abdominal wall reconstruction for a minimally invasive surgical approach (i.e., laparoscopic or robotic) hernia with Integra® Gentrix® Surgical Matrix from the prior T-GENVIH-002 study and informed consent for those who volunteer to participate.
- ✓ Creation on the CRF of a new case book for each eligible subject. Each created case book assigns the eligible subject with a study number.
- ✓ Completion of Worksheets/ CRFs: Site will transcribe/transmit the below-mentioned patients' data in study CRFs. The patients' data will originate from a direct interview with the subject by the study coordinator.
- The patients' data to be collected are:
 - ✓ Eligibility:
 - Inclusion Criteria: Ensure the subject meets all the inclusion criteria.

6.1.2 Visit 1 Questionnaire

The patients' data to be collected from the last data collection of GENVIH-002 study to date, including not previously reported, are:

- Clinically confirmed recurrence of the primary hernia repair
- Self-reported recurrence (i.e., bulge) of the primary hernia
- Surgical Site Occurrences requiring Procedural Intervention (SSOPI)
- Surgical Site Occurrences (SSOs)
- Surgical Site Infections (SSIs)

6.1.3 Adverse Events

Information will be collected on post-operative adverse events that relate to the primary hernia repair procedure, including those not previously reported in the T-GENVIH-002 study.

6.1.4 Device Deficiencies

Information will be collected for post-operative device deficiencies that relate to the primary hernia repair procedure, including those not previously reported in the T-GENVIH-002 study.

6.1.5 Study Completion/Exit

Information will be collected by the study coordinator for each enrolled subject to reflect study exit type.

6.2 Monitoring

Monitoring of the study may be conducted either remotely or in-person, as determined by the Sponsor per Sponsor's Monitoring Visit Plan.

7 Safety Assessments and Reporting

7.1 Definitions

The table below contains the definitions being used for safety assessment as part of this study:

Table 2: List of AE Terms and Definitions

This list of terms should be edited to remove those which do not concern the study.	
Term	Definition
Adverse Device Effect (ADE)	An adverse event related to the use of an investigational medical device. This definition includes adverse events resulting from insufficient or inadequate instructions for use, deployment, implantation, installation, or operation, or any malfunction of the investigational medical device. And this definition includes any event resulting from use error or from intentional misuse of the investigational device.
Adverse Event (AE)	Any untoward medical occurrence, unintended disease or injury, or untoward clinical signs (including abnormal laboratory findings) in subjects, users, or other persons, whether or not related to the investigational medical device and whether anticipated or unanticipated. This definition includes events related to the investigational medical device; events related to the procedures involved and, for users or other persons, this definition is restricted to events related to investigational medical devices.
Anticipated Serious Adverse Device Effect (ASADE)	A serious adverse device effect which by its nature, incidence, severity or outcome has been identified in the risk assessment

This list of terms should be edited to remove those which do not concern the study.

Term	Definition
Device Deficiency (DD)	
Inadequacy of a medical device with respect to its identity, quality, durability, reliability, usability, safety or performance.
 
Note 1: Device deficiencies include malfunctions, use errors, and inadequacy in the information supplied by the manufacturer including labelling.
 
Note 2: This definition includes device deficiencies related to the investigational medical device or the comparator.

Malfunction	
Failure of an investigational medical device to perform in accordance with its intended purpose when used in accordance with the instruction for use.

Serious Adverse Device Effect (SADE)	
Adverse device effect that has resulted in any of the consequences characteristic of a serious adverse event.
 
Note: SAEs related to procedures imposed by the clinical investigation plan but not with the use of the device should not be considered Serious Adverse Device Effects.

Serious Adverse Event (SAE)	
Adverse event that led to any of the following:
 
a) death,
 
b) serious deterioration in the health of the subject, users or other persons as defined by one or more of the following:
 
 a life-threatening illness or injury, or
 
 a permanent impairment of a body structure or a body function including chronic diseases, or
 
 in-patient or prolonged hospitalization, or
 
 medical or surgical intervention to prevent life-threatening illness or injury or permanent impairment to a body structure or a body function,
 
c) fetal distress, fetal death or a congenital abnormality or birth defect including physical or mental impairment.
 
Note: Planned hospitalization for a pre-existing condition, or a procedure required by the CIP, without serious deterioration in health, is not considered a serious adverse event.

This list of terms should be edited to remove those which do not concern the study.

Term	Definition
Unanticipated Adverse Device Effect (UADE)	Any serious adverse effect on health or safety or any life-threatening problem or death caused by, or associated with, a device, if that effect, problem, or death was not previously identified in nature, severity, or degree of incidence in the investigational plan or application (including a supplementary plan or application), or any other unanticipated serious problem associated with a device that relates to the rights, safety, or welfare of subjects.
Unanticipated Serious Adverse Device Effect (USADE)	
Serious adverse device effect which by its nature, incidence, severity or outcome has not been identified in the current risk assessment.
 
Note 1: Anticipated serious adverse device effect (ASADE) is an effect which by its nature, incidence, severity or outcome has been identified in the risk assessment.
 
Note 2: Procedures associated with the use of a device should be addressed in the risk assessment, which makes it possible to determine whether the procedure related SAEs are Unanticipated Serious Adverse Device Effect or not.

7.2 Reporting of Safety Information

7.2.1 Non-Reportable Event

Adverse Events not related to the primary hernia repair procedure will not be required to be reported by the investigator in this study.

7.2.2 Severity

Each adverse event will be classified according to three (3) levels of severity. The Sponsor and the investigator will use the following definitions to assess the severity of the adverse event:

Mild – Awareness of signs or symptoms, but easily tolerated and are of minor irritant type causing no loss of time from normal activities. Symptoms do not require therapy or a medical evaluation; signs and symptoms are transient.

Moderate – Events introduce a low level of inconvenience or concern to the participant and may interfere with daily activities but are usually improved by simple therapeutic measures; moderate experiences may cause some interference with functioning.

Severe – Events interrupt the participant's normal daily activities and generally require systemic drug therapy or other treatment; they are usually incapacitating.

7.2.3 Causality

The relationship between the use of the medical device (including the medical - surgical procedure) and the occurrence of each adverse event shall be assessed and categorized.

Each AE will be classified according to four (4) different levels of causality:

Not related: Relationship to the device, or procedures can be excluded when:

- the event has no temporal relationship with the use of the study devices, or the procedures related to application of the study devices;
- the serious adverse event does not follow a known response pattern to the medical device (if the response pattern is previously known) and is biologically implausible;
- the discontinuation of medical device application or the reduction of the level of activation/exposure - when clinically feasible - and reintroduction of its use (or increase of the level of activation/exposure), do not impact on the serious adverse event;
- the event involves a body-site or an organ that cannot be affected by the device or procedure;
- the serious adverse event can be attributed to another cause (e.g., an underlying or concurrent illness/ clinical condition, an effect of another device, drug, treatment or other risk factors);
- the event does not depend on a false result given by the investigational device used for diagnosis, when applicable;

In order to establish the non-relatedness, not all the criteria listed above might be met at the same time, depending on the type of device/procedures and the serious adverse event.

Possible: The relationship with the use of the investigational device or comparator, or the relationship with procedures, is weak but cannot be ruled out completely. Alternative causes are also possible (e.g., an underlying or concurrent illness/ clinical condition or/and an effect of another device, drug or treatment). Cases where relatedness cannot be assessed, or no information has been obtained should also be classified as possible.

Probable: The relationship with the use of the investigational device or comparator, or the relationship with procedures, seems relevant and/or the event cannot be reasonably explained by another cause.

Causal relationship: The serious adverse event is associated with the investigational device, or with procedures beyond reasonable doubt when:

- the event is a known side effect of the product category the device belongs to or of similar devices and procedures;
- the event has a temporal relationship with investigational device use/application or procedures;
- the event involves a body-site or organ that
 - the investigational device or procedures are applied to;
 - the investigational device or procedures have an effect on;
- the serious adverse event follows a known response pattern to the medical device (if the response pattern is previously known);
- the discontinuation of medical device application (or reduction of the level of activation/exposure) and reintroduction of its use (or increase of the level of activation/exposure), impact on the serious adverse event (when clinically feasible);
- other possible causes (e.g., an underlying or concurrent illness/ clinical condition or/and an effect of another device, drug or treatment) have been adequately ruled out;
- harm to the subject is due to error in use;
- the event depends on a false result given by the investigational device used for diagnosis, when applicable;

In order to establish the relatedness, not all the criteria listed above might be met at the same time, depending on the type of device/procedures and the serious adverse event.

The Sponsor and the investigator will distinguish between the adverse events related to the study device and those related to the procedures (any procedure specific to the study). An adverse event can be related both to procedure and the study device.

During causality assessment activity, clinical judgement shall be used and the relevant documents, such as the IFU, the Clinical Investigation Plan or the Risk Analysis Report shall be consulted, as all the foreseeable serious adverse events and the potential risks are listed and assessed there. The presence of confounding factors, such as concomitant medication/treatment, the natural history of the underlying disease, other concurrent illness or risk factors shall also be considered.

Complications caused by concomitant treatments not imposed by the clinical investigation plan are considered not related. Similarly, several routine diagnostic or patient management procedures are applied to patients regardless of the clinical investigation plan. If routine

procedures are not imposed by the clinical investigation plan, complications caused by them are also considered not related.

In some particular cases the event may not be adequately assessed because information is insufficient or contradictory and/or the data cannot be verified or supplemented. The Sponsor and the investigator will make the maximum effort to define and categorize the event and avoid these situations. Where an investigator assessment is not available and/or the Sponsor remains uncertain about classifying the adverse event, the sponsor should not exclude the relatedness; the event should be classified as “possible” and the reporting not be delayed. Particular attention shall be given to the causality evaluation of unanticipated serious adverse events. The occurrence of unanticipated events related to the use of the device could suggest that the clinical investigation places subjects at increased risk of harm than was to be expected beforehand.

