**Figure 3 : Gentrix® Surgical Matrix Thick****2.2.1 Study Device Intended Purpose**

The Gentrix® Surgical Matrix devices were used within label in this prospective study. There were no specific medical or surgical procedures involved in the use of the study devices, other than the standard of care. A full description of the medical and surgical procedures related to the Gentrix® Surgical Matrix devices is available in the Instructions for Use (IFU).

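### Protocol 7.2.3 and 7.3.1 tie procedure-relatedness to study-specific procedures, while 6.1.3, 7.2.1 and the opening of 7.2.3 mean the hernia repair, so related adverse events can be understated

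*Protocol*

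**What the plan says.** The documents use the word procedure in two senses.

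**Narrow sense.** In Protocol 7.2.3 the sponsor and investigator must distinguish device-related events from "those related to the procedures (any procedure specific to the study". The next paragraph but one notes that "several routine diagnostic or patient management procedures are applied to patients regardless of the clinical investigation plan", and where such routine "procedures are not imposed by the clinical investigation plan, complications caused by them are also considered not related". In Protocol 7.3.1 the causality field on the adverse event form is worded as the relation to the product and to the Study Procedure.

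**Broad sense.** Protocol 7.2.3 opens by assessing the relationship with "the use of the medical device (including the medical - surgical procedure", and its first criterion for non-relatedness refers to "the procedures related to application of the study devices". Protocol 7.2.1 exempts only one class of event: "Adverse Events not related to the primary hernia repair procedure will not be required to be reported". Protocol 6.1.3 collects post-operative events linked to the primary repair. The adverse event row of Table 1 is footnoted to the primary hernia surgery.

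**Status of the repair.** Protocol 2.2.1 (Study Device Intended Purpose) says of it: "There were no specific medical or surgical procedures involved in the use of the study devices, other than the standard of care". The synopsis gives the study intervention as a single interview with a questionnaire. Section 5.6.2 says that participation adds no procedures beyond usual care, and sections 2.2.4 and 2.2.5 call the study noninterventional.

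**The concern.** The narrow sense suits a trial whose plan prescribes the operation. Here the operation took place before the study and outside its plan, so defining procedure by what the study imposes leaves out the one procedure whose complications the study wants to learn about. The safety objective in Protocol 3.2 is to capture complication "data in the later post-operative period to date, not previously reported in the T-GENVIH-002 study". Many such events will be attributed to the surgery rather than to the matrix.

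What is at stake is the causality coding and the outputs that rest on it. These are the count and percentage of subjects with any related adverse event (Protocol 10.4.5) and the tabulation by relationship to device and procedure (SAP 9.3.4). Completeness of the adverse event form is a lesser concern, because Protocol 7.3.1 requires the form for potentially device- or procedure-related events without saying which procedure is meant.

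**Working it through.** The plan states no figure on this point, so the check is a reconciliation of text.

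**Step 1: what is specific to the study?** The synopsis lists one interview. Section 5.6.2 adds no procedure or exam. The repair preceded the study and was standard of care. The set of study-specific procedures is therefore the interview alone, and under the narrow sense the procedure-related category is practically empty.

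**Step 2: which section uses which sense?**

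| Place | Procedure means |
|---|---|
| Protocol 6.1.3 | primary hernia repair |
| Protocol 7.2.1 | primary hernia repair |
| Protocol 7.2.3, opening and first non-relatedness criterion | surgical procedure applying the device |
| Protocol 7.2.3, device versus procedure distinction | study-specific procedures only |
| Protocol 7.3.1, duty to report | not defined |
| Protocol 7.3.1, causality field | Study Procedure |
| SAP 9.3.4 | not defined |

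Section 7.2.3 thus carries both senses, and neither 7.3.1 nor SAP 9.3.4 settles the matter.

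**Step 3: follow one event.** Take chronic pain that the investigator attributes to the operation and not to the matrix.
- *Broad sense:* procedure-related. It counts in any related event and in the procedure column, and it goes on the form.
- *Narrow sense:* not procedure-related, and not device-related either. It leaves the related count. Section 7.2.1 still supports reporting it, because that section names the repair. Section 7.3.1, read with the narrow sense, does not require it. Section 7.3.3 does not break the tie: it defines reportable events by pointing back to 7.2.1, which states only an exemption.

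Events with a possible link to the matrix are related under either sense. Only events attributed to the operation alone are exposed.

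**Step 4: which outputs depend on the coding?** Protocol 10.4.5 and SAP 9.3.4 use relatedness directly. SAP 9.3 takes the primary, secondary and safety endpoints from the Visit 1 Questionnaire, and no causality filter is stated there. Recurrence, SSO, SSI, SSOPI and reoperation are therefore not directly affected. However, the complication list in Protocol 3.2 is open-ended, and Protocol 7.2.4 anticipates events such as chronic pain, adhesions and bowel injury that the questionnaire items in 6.1.2 do not name. For these the adverse event form is the named route.

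**Step 5: scale.** The planned size is about 21 (Protocol 10.2, SAP section 8). One subject recoded from related to unrelated changes a percentage by 1/21 = 0.048, or 4.8 percentage points, if all 21 are in the denominator. The documents do not allow an estimate of how many subjects would be recoded.

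**The case against.** A reader might infer that complications of the repair become unrelated and therefore non-reportable. The documents do not support that.
- Sections 6.1.3 and 7.2.1 name the primary hernia repair, so they favour collecting and reporting its complications whatever 7.2.3 says later.
- The exclusion sentence in 7.2.3 refers back to routine diagnostic or patient management procedures. Extending it to the operation that implanted the device is arguable.
- The opening of 7.2.3 includes the surgical procedure.
- The wound events that the safety objective lists are the SSO endpoint, which comes from the questionnaire.

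There are also safeguards. Sections 7.2.3 and 7.3.1 lean toward inclusion: relatedness that cannot be assessed is classed as possible, and potentially related events must be reported. Assessors are sent to the instructions for use, whose anticipated events in 7.2.4 include infection, seroma, fistula, hematoma and recurrence.

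Most of this stands, and it limits the point to causality coding and possible gaps on the form. It does not remove the conflict. The default to possible covers missing, insufficient or contradictory information and sponsor uncertainty; a site that follows the study-specific wording is applying a categorical rule and need not feel uncertain. That wording is not limited to diagnostic or management procedures, so it creates the conflict even if the exclusion sentence never reaches the repair. The causality field in 7.3.1 sits closer to the narrow sense than to 7.2.1.

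**Conclusion.** The inconsistency is real and should be resolved before causality is coded. Followed literally, the narrow wording lets repair complications be coded as unrelated to procedure. That would understate any related event in Protocol 10.4.5 and the relationship table in SAP 9.3.4, and could leave some events that are not questionnaire items off the form. The direction is downward. The amount is unknown beyond the 4.8 points per subject, which assumes a full denominator of 21.

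The conclusion assumes that at least some complications would be attributed to the operation and not to the matrix, and that some assessors would apply the study-specific wording. The study is descriptive with no hypothesis test, so no inferential result is at risk, and the questionnaire-based endpoints are not directly touched.

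**What to change.** Reconcile the sections around one meaning:
- In Protocol 7.2.3, replace the study-specific parenthesis with the index (primary) hernia repair, including implantation of the matrix.
- In the same section, state that the exclusion for routine procedures outside the plan does not apply to the index repair.
- In Protocol 7.3.1, on the adverse event form and in SAP 9.3.4, use that same meaning; in particular, replace Study Procedure in the causality field.

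Sections 6.1.3 and 7.2.1 already name the repair and need no change of meaning.

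The cost is a few sentences in the protocol and SAP and one field label on the form, with no change to visits or treatment. Slightly more events will be recorded as procedure-related.
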